4.4.5. Prior and Concomitant Therapy

Information about prior medications, including hormonal contraceptives, taken by the subject in the 30 days prior to providing informed consent will be recorded on the appropriate DCF.

Concomitant medications include all medications (prescription, over the counter, supplements, and vaccines received outside of the study) taken by the subject from the time the informed consent is signed through Day 394. At each study visit following dosing, including telephone calls, subjects will be queried about new concomitant medications and changes to existing medications.

Medications that might interfere with the evaluation of the investigational product should not be used by the subject during the study-reporting period (12 months after the last vaccination) unless clinically indicated as part of the subject's health care.

In the event medical conditions dictate the use of medications, subjects are encouraged to obtain adequate care, comply with the course of therapy as prescribed by their physician, and inform the study Investigator as soon as practical. Any drug or vaccine used or received by the subject during the trial should be recorded on the appropriate DCF.

4.4.6. Treatment Compliance

All subjects are to receive 2 doses of study product administered in the clinic.

5. SAMPLE SIZE CONSIDERATIONS

Rare AEs are not demonstrable in a clinical study of this size; however, the probabilities of observing one or more AEs given various true event rates are presented in [Table 3](#). With the assumption that all enrolled subjects will likely complete immunizations and safety visits in this relatively short duration study, the following statistical considerations apply. With 15 subjects in each dose group (cohorts 1-3,10,13), the chance of observing at least one AE of probability 20% or more is approximately 97%. Therefore, if no AEs of a given type occur in a dose group (cohorts 1-3,10,13), we can be relatively confident that they will occur in fewer than 20% of people once the vaccine is implemented. With 60 subjects across these four dosing cohorts (1-3,10), the chance of observing at least one AE of probability 5% or more is at least 95%. Therefore, if no AEs of a given type occur across the combined doses, we can be very confident that any dosage-independent event will occur in fewer than 5% of people once the vaccine is implemented. If Cohort 13 is enrolled and there are 75 subjects across five dosing cohorts (1-3,10,13), the chance of observing at least one AE of probability 5% or more is at least 97.9%. Therefore, if no AEs of a given type occur across the combined doses, we can be very confident that any dosage-independent event will occur in fewer than 5% of people once the vaccine is implemented. With 10 subjects in each dose group (cohorts 4-9,11-12), the chance of observing at least one AE of probability 20% or more is approximately 89.3%. Therefore, if no AEs of a given type occur in a dose group (cohorts 4-9,11-12), we can be relatively confident that they will occur in fewer than 20% of people once the vaccine is implemented in the older population. With 30 subjects across each of the two older subject dosing cohorts (i.e., cohorts 4,5,11 and 7,8,12), the chance of observing at least one AE of probability 5% or more is at least 78.5%. Therefore, if no AEs of a given type occur across the combined doses, we can be very confident that any dosage-independent event will occur in fewer than 5% of older people once the vaccine is implemented. If Cohorts 6 and 9 are enrolled and there are 40 subjects across each of the two older subject dosing cohorts (i.e., cohorts 4,5,6,11 and 7,8,9,12), the chance of observing at least one AE of probability 5% or more is at least 87.1%. Therefore, if no AEs of a given type occur across the combined doses, we can be very confident that any dosage-independent event will occur in fewer than 5% of older people once the vaccine is implemented.

6. GENERAL STATISTICAL CONSIDERATIONS

6.1. General Principles

All continuous variables will be summarized using the following descriptive statistics: n (non-missing sample size), mean, standard deviation, median, maximum and minimum. The frequency and percentages (based on the non-missing sample size) of observed levels will be reported for all categorical measures. In general, all data will be listed, sorted by site, treatment and subject, and when appropriate by visit number within subject. All summary tables will be structured with a column for each treatment and will be annotated with the total population size relevant to that table/cohort, including any missing observations.

6.2. Analysis Populations

6.2.1. Modified Intention-to-Treat (mITT) Population

The modified intent-to-treat (mITT) population includes all subjects who received one dose of vaccine and contributed both pre- and at least one post-vaccination venous blood samples for immunogenicity testing for which valid results were reported.

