- b) Clinical screening laboratory evaluations will include WBCs, Hgb, PLTs, Cr, ALT, AST, ALP, T. Bili, Lipase, PT, PTT, hepatitis B surface antigen, hepatitis C virus antibody, and HIV types 1 and 2 antigen/antibody. Clinical safety laboratory evaluations obtained on Days 1, 8, 29, and 36 will include WBCs, Hgb, PLTs, Cr, ALT, AST, ALP, T. Bili, and Lipase.
- c) For women of childbearing potential serum pregnancy test at screening, and urine or serum pregnancy test on Days 1 and 29 with results confirmed as negative prior to enrollment on Day 1 and administration of each vaccination.
- d) Depending on the timepoint approximately 8 or 16 mL of each venous blood sample is designated for secondary research.
- e) For those subjects consented for leukapheresis, screening procedures, including screening laboratory evaluations, will be performed locally prior to the leukapheresis procedure. Refer to the protocol-specific MOP for details on the leukapheresis procedure.
- f) Visits 09-14 windows should be based off the actual Visit 06 date.
- g) Subjects who participate in the optional third mRNA-1273 vaccination substudy will exit the Schedule of Activities for the main study between Visit 13 and the close of the window for Visit 14 and will not have Visit 14, instead will have Visit 14A and subsequent substudy visits. See [Section 12](#), Appendix A for the Schedule of Activities for the optional third mRNA-1273 vaccination substudy.

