## 4.4 Optional Third mRNA-1273 Vaccination Substudy

All subjects in this clinical trial were scheduled to receive two mRNA-1273 vaccinations, 28 days apart, at dosages of 25, 50, 100, or 250 mcg (see [Table 1](#)), with the last scheduled follow-up visit occurring at 365 days after the second vaccination (see [Table 4](#)). During the course of the main study, interim efficacy data from a Phase 3 placebo-controlled clinical trial of mRNA-1273 (COVE), administered as 2 doses of 100 mcg given 28 days apart, demonstrated vaccine efficacy of 94.1% (95% CI: 89.3%, 96.8%) for the prevention of symptomatic, confirmed COVID-19

(Baden, LR, et al. 2020). After review of the interim safety and efficacy data from that clinical trial, the FDA granted on December 18, 2020 an Emergency Use Authorization (EUA) for the mRNA-1273 vaccine in adults 18 years of age and older.

To potentially enhance and extend the duration of protection provided by the 2-dose vaccination schedule of mRNA-1273 administered in the main study, and to gain an understanding of the immune responses to a third dose of mRNA-1273, subjects in the main study may participate in an optional third mRNA-1273 vaccination substudy, detailed in [Section 12, Appendix A](#). Substudy subjects will receive a third mRNA-1273 vaccination, administered via an IM injection at a dosage of 100 mcg/0.5 mL, given six to twelve months after receipt of their second vaccination in the main study. Substudy subjects will be followed for safety, reactogenicity, and immunogenicity endpoints through 12 months post third vaccination (Substudy Day 366).

To be eligible to participate in the substudy, subjects must have received both the first and second mRNA-1273 vaccinations in the main study. Other eligibility criteria are specified in [Appendix A](#). Subjects who received only one mRNA-1273 vaccination in the main study will be advised to receive an FDA authorized or approved COVID-19 vaccine, according to the recommended schedule, when available to them outside of this trial, unless they have a contraindication to COVID-19 vaccines that are available.

Subjects who elect not to participate in the optional third mRNA-1273 vaccination substudy or are not eligible for the substudy will continue to be followed according to the Schedule of Activities for the main study (see [Table 4](#)) with the Final Study Visit 14 occurring at Day 394 ( $\pm 14$  days).

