### 9.3 Populations for Analyses

The Safety Analysis population for the main study includes all subjects who received one dose of vaccine. Analyses for the primary safety population will include safety reported through the end of the main study. A modified primary safety population analysis will also be performed that excludes safety data collected after subjects receive either the third mRNA-1273 vaccination in the optional substudy or non-study EUA vaccine, if applicable.

The modified intent-to-treat (mITT) population includes all subjects who received one dose of vaccine and contributed both pre- and at least one post-vaccination venous blood samples for immunogenicity testing for which valid results were reported.

In the final analysis, protocol deviations will be reviewed to determine which protocol deviations may affect the analysis. The per protocol (PP) population will then be defined – and this includes all subjects in the mITT subset with the following exclusions:

- Data from all available visits for subjects found to be ineligible at baseline.
- Data from all visits subsequent for the protocol deviations that are considered to affect the science.

- Data from any visit that occurs substantially out of window.

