Subjects who receive the third mRNA-1273 vaccination will exit the Schedule of Activities for the main study and will enter the Schedule of Activities for the optional third mRNA-1273 vaccination substudy (see [Table 14](#)). Substudy follow-up visits will occur 1, 2 and 4 weeks post the third mRNA-1273 vaccination (Substudy Days 8, 15, and 29), as well as 3, 6 and 12 months after the third mRNA-1273 vaccination (Substudy Days 91, 181 and 366). Blood will be drawn at these substudy visits for immunogenicity assays. As with prior mRNA-1273 vaccinations, reactogenicity will be measured by the occurrence of solicited injection site and systemic reactions from the time of the third mRNA-1273 vaccination through 7 days after the third mRNA-1273 vaccination. Unsolicited non-serious AEs will be collected from the time of the third mRNA-1273 vaccination through 28 days after the third mRNA-1273 vaccination. SAEs, Protocol Specified AESIs, MAAEs, and NOCMCs will be collected from the time of first mRNA-1273 vaccination through 12 months after the third mRNA-1273 vaccination.

Subjects who do not participate in this substudy, including those who are not eligible to participate in the substudy due to their prior receipt of an FDA authorized (under an EUA) or approved COVID-19 vaccine outside of this clinical trial, will continue, with their permission, to be followed according to the Schedule of Activities for the main study (see [Table 4](#)).

Interim safety and immunogenicity data from this substudy may be reviewed as needed, at the discretion of the study team, to inform public health decisions and to assess the adequacy of the immune responses in the 25 and 50 mcg dose cohorts compared with the 100 mcg dose cohort. Information from interim data reviews may be disseminated to public health officials and partners as needed and included in publications and presentations to inform the global scientific community.

Evaluation of immunogenicity will include quantitation of antibodies to the SARS-CoV-2 S protein at multiple timepoints post third mRNA-1273 vaccination as measured by ELISA and virus neutralization assays. In addition, exploratory studies to characterize T cell responses are planned.

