### 12.6.2 Exclusion Criteria

A subject who meets any of the following criteria will be excluded from participation in this substudy.

1. Anaphylaxis or other systemic hypersensitivity reaction following a mRNA-1273 or any other vaccination.
2. Immediate allergic reaction of any severity after mRNA-1273 or any of its components.

Including polyethylene glycol (PEG)

3. Immediate allergic reaction of any severity to polysorbate.

Due to potential cross-reactive hypersensitivity with the vaccine ingredient PEG

4. History of an SAE judged related to mRNA-1273 vaccine.
5. Female subject who is breastfeeding or plans to breastfeed from the time of the third mRNA-1273 vaccination through 30 days after the third mRNA-1273 vaccination.
6. Has an acute illness, as determined by the participating site PI or appropriate sub-investigator, with or without fever [oral temperature  $\geq 38.0^{\circ}\text{C}$  ( $100.4^{\circ}\text{F}$ )], within 72 hours prior to the third mRNA-1273 vaccination.

An acute illness which is nearly resolved with only minor residual symptoms remaining is allowable if, in the opinion of the participating site PI or appropriate sub-investigator, the residual symptoms will not interfere with the ability to assess safety parameters as required by the substudy.

7. Has received any approved, authorized or investigational COVID-19 vaccine outside of this trial.
8. Any clinically significant medical condition that, in the opinion of the investigator, poses an additional risk to the subject from vaccination.
9. History of documented COVID-19 infection.
10. Has any medical disease or condition that, in the opinion of the participating site PI or appropriate sub-investigator, precludes substudy participation.
11. Received or plans to receive a licensed vaccine, other than a COVID-19 vaccine, within 2 weeks before or after the third mRNA-1273 vaccination.

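### Late exploratory mITT titers can include a response to a non-study COVID-19 vaccine, and the modified safety analysis in Protocol 9.3 has no immunogenicity counterpart

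*SAP*

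**What the plan says.** **Safety.** Protocol 9.3 keeps an unrestricted analysis: "Analyses for the primary safety population will include safety reported through the end of the main study". It then adds a modified one that "excludes safety data collected after subjects receive either the third mRNA-1273 vaccination in the optional substudy or non-study EUA vaccine". SAP 6.2.3 defines only the plain safety population and does not mention the modified analysis.

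**Immunogenicity.** Protocol 9.3 and SAP 6.2.1 define the mITT in the same words: it "includes all subjects who received one dose of vaccine and contributed both pre- and at least one post-vaccination venous blood samples". This selects subjects, not samples. SAP 6.4, 8.2 and 8.3 add no rule for samples drawn after another vaccine. SAP 8.2 and 8.3 make the mITT the population for immunogenicity summaries and leave a per-protocol (PP) analysis optional.

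**Outside vaccination.** Under Protocol 4.4, subjects who received only one study dose "will be advised to receive an FDA authorized or approved COVID-19 vaccine, according to the recommended schedule, when available to them outside of this trial". Subjects with a contraindication are excepted. Item 7 of Protocol 12.6.2 bars from the substudy anyone who "Has received any approved, authorized or investigational COVID-19 vaccine outside of this trial". Under Protocol 12.5, subjects who do not enter the substudy, including those barred for this reason, "will continue, with their permission, to be followed according to the Schedule of Activities for the main study". That schedule draws immunogenicity serum at Days 209 and 394. Substudy participants, by note g to Table 4, "will not have Visit 14, instead will have Visit 14A and subsequent substudy visits".

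**The concern.** The protocol treats an outside vaccine as important enough to justify a second safety analysis, yet it is silent on titers, which another spike vaccine would affect directly. IgG at every timepoint other than Day 57 is an exploratory endpoint, and Protocol 12.2 calls durability beyond three months uncertain. Days 209 and 394 are the visits that would inform it. If some samples there follow a non-study dose, possibly mRNA-1273 given under the EUA, the mITT summary mixes persistence after the study doses with a response to another dose, and nothing planned separates the two.

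Day 394 is the most exposed visit. Substudy participants are absent from it, while subjects vaccinated outside are barred from the substudy and may remain. The Day 394 sample can therefore be both small and enriched for outside vaccinees.

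**Working it through.** The plan gives no figure to reproduce on this point. The check has two parts: which visits can be affected, and how the cohort GMT responds.

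**1. Timing**

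Inputs from the documents:
- Protocol 4.4 dates the mRNA-1273 EUA December 18, 2020.
- Protocol 12.2 says two mRNA vaccines received EUAs in December 2020. Only one is dated, so December 1 serves as the earliest bound.
- Protocol 5 estimates about 16 weeks to complete enrolment.
- The amendment history, used only for dates, puts version 2.0 at March 13, 2020 and version 4.0, which added cohorts 10-12, at May 20, 2020.

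Assumption: no enrolment dates are given, so Day 1 is taken to run from March 13 to July 3, 2020 (16 weeks). Day d falls d − 1 days after Day 1.

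| Visit | Earliest | Latest | Against December 2020 |
|---|---|---|---|
| Day 57 | May 8, 2020 | Aug 28, 2020 | before |
| Day 119 | Jul 9, 2020 | Oct 29, 2020 | before |
| Day 209 | Oct 7, 2020 | Jan 27, 2021 | straddles |
| Day 394 | Apr 10, 2021 | Jul 31, 2021 | after |

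A Day 209 sample falls on or after an EUA date only if Day 1 was on or after May 7, 2020 (December 1 bound) or May 24, 2020 (December 18). Cohorts 10-12, starting no earlier than May 20, reach Day 209 no earlier than December 14, 2020, so they are the main Day 209 exposure.

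Sensitivity: with 20 weeks of enrolment the last Day 119 is November 26, 2020, still before. With 24 weeks it is December 24, 2020, six days after the mRNA-1273 EUA, while the last Day 57 is October 23, 2020. SAP 6.5 uses cohorts 10-12 only to Day 57 in the interim report.

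**2. Effect on a cohort GMT**

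The log GMT is the mean of the log titers. If k of the n subjects sampled at a visit have titers raised f-fold, that mean rises by (k/n)·log f, so the GMT is multiplied by f^(k/n). Here n is the number actually sampled at that visit, not the cohort size at enrolment.

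All of f, k and the reduced n are assumptions; the documents give none of them.

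| k of n | f = 4 | f = 10 | f = 30 |
|---|---|---|---|
| 1 of 10 (full older cohort) | 1.15 | 1.26 | 1.41 |
| 1 of 5 (assumed remaining) | 1.32 | 1.58 | 1.97 |
| 2 of 5 (assumed remaining) | 1.74 | 2.51 | 3.90 |

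At 10-fold: 10^(1/10) = 1.26 and 10^(2/5) = 2.51.

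**3. Direction**

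Protocol 12.2 considers robust serological responses to revaccination likely, even after the lower study doses. Protocol 12.2.1 says it is not known whether a third dose will elicit a response. Upward within a subject is therefore the likely direction, but it is not established.

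**The case against.** The strongest reply is that the PP population already does this work. SAP 6.2.2 removes visits that follow deviations judged to affect the science. The SAP lists a PP table beside each mITT IgG table. The shell of SAP Table 13 carries a template note about removing visits after Day 29. Main exclusion 21 covers receipt of another SARS-CoV-2 vaccine during the study, which gives a basis for calling it a deviation. Listings 8 and 17 show sample day and medication start day, so affected samples can be found. The outputs are exploratory and descriptive, and no hypothesis is tested.

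Most of this is accurate, and it limits the point. It does not close the gap. The text of SAP 8.2 and 8.3 leaves the PP analysis optional. Neither document says whether outside vaccination is a deviation, or whether mRNA-1273 given under the EUA counts as another vaccine under exclusion 21. A one-dose subject who follows the advice in Protocol 4.4 is hard to call a deviator without further text. The Table 13 note is a template and gives no reason for removal. The mITT summaries stay unfiltered whatever happens in the PP set.

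Exposure is also only partly documented. Protocol Table 13 records four one-dose subjects (two in cohort 1, one each in cohorts 3 and 5). Three of them stopped for adverse events, and the advice excepts contraindications. No two-dose subject is recorded as vaccinated outside, and two-dose subjects were offered a third dose within the trial.

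**Conclusion.** The point stands as a missing rule for late exploratory titers. Followed as written, the mITT can put responses to a non-study dose into Day 394 summaries, and into Day 209 summaries for later-enrolled subjects. The timing rests on the assumed enrolment dates. The omission of the modified safety analysis from SAP 6.2.3 is a separate gap, and it touches the primary endpoint.

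Four stronger readings are tempting and not supported:

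- **That the late GMTs are inflated by a known amount.** Uptake, fold rise and the number remaining at Day 394 are not documented, so the factors above are illustrations. An upward shift within a one-dose subject also does not show that the cohort GMT ends above what two doses would have given.
- **That the secondary endpoint is affected.** Day 57 precedes both EUA bounds under the assumed dates, and also with 24 weeks of enrolment. The interim report is likewise unaffected under the assumed dates.
- **That third study doses contaminate the main-study titers.** Substudy participants leave the main schedule after Visit 13 and have no Visit 14.
- **That the mITT definition is wrong.** The safety precedent keeps the full analysis and adds a second one; the same suffices here.

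**What to change.** In the SAP:

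- Keep the mITT and its summaries as defined.
- In 6.2 and 8.2-8.3, add a summary of Day 209 and Day 394 titers that excludes samples drawn after a recorded non-study COVID-19 vaccine, with n per cohort and visit. The IgG shells stop at Day 119, so the late tables have to be specified in any case.
- In 6.2.2, state whether receipt of such a vaccine, including mRNA-1273 under the EUA, removes later visits from the PP population.
- In 6.2.3, carry over the modified safety analysis from Protocol 9.3.

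Main exclusion 21 (Protocol 5.2) and the advice in Protocol 4.4 must be reconciled, so that the status of outside vaccination is clear.

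The cost is SAP wording, one date flag and one more table set. Protocol 6.5 already has outside vaccines recorded through Day 394, so no new data are needed. The downside is fewer samples in the added late summaries, which may be few at Day 394 once substudy participants have left.

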6.2.2. Per Protocol Population

In the final analysis, protocol deviations will be reviewed to determine which protocol deviations may affect the analysis. The per protocol (PP) population will then be defined – and this includes all subjects in the mITT subset with the following exclusions:

- Data from all available visits for subjects found to be ineligible at baseline.
- Data from all visits subsequent for the protocol deviations that are considered to affect the science.
- Data from any visit that occurs substantially out of window.

